3.5 Discontinuation of Subjects following any Treatment with Study Drug

Subjects MUST discontinue investigational product (and non-investigational product at the discretion of the investigator) for any of the following reasons:

- Subject's request to stop study treatment
- Any clinical adverse event (AE), laboratory abnormality or intercurrent illness which, in the opinion of the investigator, indicates that continued participation in the study is not in the best interest of the subject
- Termination of the study by Bristol-Myers Squibb (BMS)
- Loss of ability to freely provide consent through imprisonment or involuntarily incarceration for treatment of either a psychiatric or physical (eg, infectious disease) illness
- Repeat non-adherence by the subject with the requirements of the protocol or treatment (as determined by Investigator in consultation with the BMS Medical Monitor)
- Evidence of Hepatitis B or C infection
- Confirmed plasma HIV-1 RNA \geq 1000 c/mL after Week 24
- Confirmed plasma HIV-1 RNA \geq 200 c/mL after Week 48
- Emergence of genotypic and/or phenotypic resistance to any component of the study treatment regimen at any time after Screening
- Subject requires switching to any other ARV
- Development of pDILI (potential drug induced liver injury)

- Confirmed QTcB or QTcF value > 500 msec
- Confirmed second degree (Type II) or third degree AV block at any time during the study

In the case of pregnancy, the investigator must immediately notify the BMS Medical Monitor/designee of this event. In most cases, the study drug will be permanently discontinued in an appropriate manner. If the investigator determines a possible favorable benefit/risk ratio that warrants continuation of study drug, a discussion between the investigator and the BMS Medical Monitor/designee must occur.

All subjects who discontinue study drug should comply with protocol specified follow-up procedures as outlined in [Section 5](#) (ie, perform an Early Termination [ET] visit). The only exception to this requirement is when a subject withdraws consent for all study procedures including post-treatment study follow-up (no such period exists in this study) or loses the ability to consent freely (ie, is imprisoned or involuntarily incarcerated for the treatment of either a psychiatric or physical illness).

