5.4.1.1 Guidelines for Confirmatory Testing of Plasma HIV-1 RNA and Resistance testing

A confirmatory HIV-1 RNA viral load should be obtained when:

- HIV-1 RNA \geq 40 c/mL if prior suppression $<$ 40 c/mL, or
- $> 1 \log_{10}$ c/mL increase in HIV-1 RNA at anytime above nadir level where nadir is \geq 40 c/mL

All efforts should be made to collect this sample within 2-4 weeks from the collection of the original sample.

When collecting a blood sample for HIV-1 RNA testing at an Unscheduled visit, samples should also be collected for the sets of Resistance and Exploratory Resistance Tests, so that the samples are available should resistance testing be required or deemed necessary based on the result of the HIV-1 RNA test.

Table 5.4.1.1-1: Management of Detectable HIV-1 RNA, based on Confirmed (2-4 weeks from original sample) or Consecutive HIV-1 RNA Result^a

Day 1 through Week 24	
40 - 399 c/mL	Reinforce Adherence
\geq 400 c/mL	Consider the need for resistance testing, in consultation with BMS Medical Monitor. Consider possible discontinuation of subject, in consultation with BMS Medical Monitor, and/or reinforce adherence.
After Week 24 through Week 48	
40 - 399 c/mL	Reinforce Adherence
400 - 999 c/mL	Resistance testing will be performed. If resistance has developed, subject must be discontinued. If resistance has not developed, consider possible discontinuation of subject, in consultation with BMS Medical Monitor, and/or reinforce adherence.
\geq 1000 c/mL	Resistance testing will be performed. Regardless of result of resistance tests, subject must be discontinued (see Section 3.5).
After Week 48	
< 200 c/mL	Reinforce Adherence
\geq 200 c/mL	Subject must be discontinued (see Section 3.5). If \geq 400 c/mL, consider the need for resistance testing, in consultation with BMS Medical Monitor.

^a When discontinuation is required or otherwise warranted and resistance results are needed, subject may continue on study medication/on study until resistance testing results are available.

5.4.1.2 *Protocol Defined Virologic Failure*

Protocol Defined Virologic Failure (PDVF) is defined by a subject meeting one of the following three criteria:

- 1) Confirmed $> 1 \log_{10}$ c/mL increase in HIV-1 RNA at anytime above nadir level where nadir is ≥ 40 c/mL
- 2) Confirmed HIV-1 RNA ≥ 400 c/mL after Week 24
- 3) Failure to suppress last HIV-1 RNA to < 400 c/mL within Week 24, 48, or 96 week snapshot window

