In addition to the clinical management outlined in [section 5.4.1.1](#), samples meeting criteria for PDVF will also be sent for resistance and exploratory resistance testing.

5.4.2 *Secondary Efficacy Assessments*

5.4.2.1 *CD4+ and CD8+ T-Cells*

CD4+ and CD8+ T-cells counts and percentages will be assessed using flow cytometry. The schedule of assessments is provided in [Section 5.1](#) (Flow Chart/Time and Events Schedule). Procedures for samples collection and processing are provided in the central clinical laboratory manual.

5.4.2.2 *Drug Resistance Testing*

Plasma samples for viral drug resistance testing will be collected at Screening for all subjects and the HIV-1 drug resistance genotype will be analyzed to rule out resistance to any component of the study regimen or specific resistance mutations as outlined in [Section 3.3.2](#), Exclusionary Criteria. At subsequent visits, samples for emergent drug resistance testing (both genotypic and phenotypic) will be collected and stored to be as outlined in [Section 5.4.1](#).

5.5 *Pharmacokinetic Assessments*

It is extremely important to record the exact dose and time of the dose(s) taken the day prior to the visit/collection, and the exact date and time of the sample collection, even if drawn slightly off-schedule.

5.5.1 *Intensive Pharmacokinetic Assessment*

A subset of subjects (about 12 subjects per treatment group) will participate in an optional Intensive PK assessment at Week 2 (window Day 12-16).

Intensive PK samples collected in this study will provide for the assessment of BMS-955176, ATV, RTV, and DTG to support the secondary and exploratory objectives (to characterize the PK of BMS-955176, DTG, and ATV (with or without RTV) when given in combination, and to compare steady-state exposures of DTG when co-administered with BMS-955176 and ATV/RTV to DTG when co-administered with TDF and ATV/RTV).

Intensive PK sampling begins with a morning pre-dose (0 hour) sampling, ie, prior to the administration of the morning doses of the study drugs on the day of the visit. The sampling

should also begin 24 hours after the morning doses of the study drugs that were taken the day prior to the visit.

The subsequent 11 time points include samplings through Hour 12, with the last sample collected at Hour 24. The subject will either stay overnight or will return to the clinic so that the final sample can be collected at Hour 24.

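### After Week 48 a confirmed viral load of 200-399 c/mL forces discontinuation but meets no virologic-failure criterion and prompts no resistance test, so the failure tally and the resistance tabulation may miss these subjects

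*Protocol*

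**What the plan says.** All references are to Revised Protocol 01.

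- **Stop rule.** Section 3.5 lists a confirmed plasma HIV-1 RNA at or above "200 c/mL after Week 48" among the mandatory reasons to discontinue. The last row of Table 5.4.1.1-1 repeats it: "subject must be discontinued (see Section 3.5").
- **Resistance testing in that table.** After Week 48, testing is mentioned only from 400 c/mL upward, and only as advice. The wording is the same as for that level in the Day 1 to Week 24 row: "Consider the need for resistance testing, in consultation with BMS Medical Monitor". In the rows for Weeks 24 to 48, testing from 400 c/mL upward is mandatory.
- **PDVF (Section 5.4.1.2).** There are three criteria: a confirmed rise of more than 1 log10, worded as "increase in HIV-1 RNA at anytime above nadir level where nadir is" at least 40 c/mL; "Confirmed HIV-1 RNA ≥ 400 c/mL after Week 24"; and "Failure to suppress last HIV-1 RNA to < 400 c/mL within Week 24, 48, or 96 week snapshot window".
- **Consequence of PDVF.** Directly after the criteria the protocol states, as an addition to the clinical management in Section 5.4.1.1, that "samples meeting criteria for PDVF will also be sent for resistance and exploratory resistance testing".
- **Use in the analysis.** The secondary resistance objective (Section 1.3.2) is confined to samples selected by the Section 5.4.1 criteria. The endpoint (Section 8.3.2) is confined to samples sent for testing. Section 8.4.2.2 tabulates emergent substitutions and phenotypic resistance by arm from on-treatment isolates.

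**The concern.** Between Weeks 24 and 48 the thresholds are in a workable order. Testing is mandatory from 400 c/mL and the viral-load stop comes at 1000 c/mL, so anyone stopped by that rule has already passed the testing level. After Week 48 the order is reversed: the stop comes at 200 c/mL, and failure and testing begin at 400 c/mL. The stop can therefore remove a subject for loss of virologic control before the failure definition, or the testing it triggers, can apply. Section 3.5 states that the study has no post-treatment follow-up period, so a later on-treatment value that reaches 400 c/mL is not normally to be expected.

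What is at stake is how completely late resistance is ascertained. Section 1.1.1 justifies 96 weeks of treatment by durability of response, and Section 1.1.3 says that Arms 3 and 4 may be more prone to resistance than Arm 1. If testing of late removals is left to judgement in an open-label trial, those who decide know the arm, and ascertainment could differ between arms.

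**Working it through.** The protocol's only sample-size figure is an exact 95% interval of roughly 64% to 91% for 80% response in 40 subjects. It reproduces (32/40 gives 64.4% to 90.9%), but the present point does not depend on it. The check here compares thresholds.

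**Inputs.** Stop after Week 48: confirmed value V of at least 200 c/mL (Section 3.5, Table 5.4.1.1-1). PDVF criteria 1 to 3: Section 5.4.1.2. Snapshot cut-offs: below 40 and below 200 c/mL (Section 8.3.2), with all treated subjects in the denominator (Section 8.4.2.1).

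**Can a confirmed V of 200-399 c/mL be PDVF?**

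- Criterion 1 needs log10(V) - log10(nadir) > 1, that is V > 10 × nadir. The nadir must be at least 40, so V must exceed 10 × 40 = 400. At the top of the band, 399/40 = 9.975, which is below 10. A subject whose nadir was below 40 is outside this criterion altogether.
- Criterion 2 needs V of at least 400, which no value in the band reaches.
- Criterion 3 needs the last value in the window to be 400 or more, which again no value in the band reaches.

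Checking every whole number from 200 to 399, against every whole-number nadir from 40 to 399 for criterion 1, gives 0 of 200 values meeting any criterion.

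**Does Table 5.4.1.1-1 prompt a test?** No. After Week 48 its only mention of testing is at 400 c/mL or more.

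**Is the value a snapshot response?** No. None of the 200 values is below 40 or below 200. A subject stopped in this band before the Week 96 window stays in the denominator as a Week 96 non-responder at both cut-offs.

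**How many subjects?** The protocol gives no rate. As an assumption, 0, 1, 2 or 4 removals per arm of 40 would put 0/40 = 0%, 1/40 = 2.5%, 2/40 = 5% or 4/40 = 10% of the arm outside PDVF and outside prompted testing. The snapshot failure count is the same in every case.

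**The case against.** Much can fairly be said for the plan.

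- **Testing is possible.** A reader might infer that these subjects can never be tested. The documents do not support that. Table 5.1-2 has resistance samples stored at scheduled in-clinic visits and/or early termination, and Section 5.4.1.1 has them collected with every unscheduled HIV-1 RNA. Section 5.9 allows on-treatment samples to be tested when judged clinically relevant, with no viral-load floor. This stands. What is missing is a rule, and a discretionary route is a weak basis for a by-arm tabulation in an open-label trial.
- **Late efficacy is protected.** A reader might also infer that late failure is under-counted in the efficacy results. It is not: the Week 96 snapshot already counts these subjects as non-responders, and PDVF is not a listed endpoint. This stands in full. The snapshot does not, however, supply a resistance result.
- **PDVF is not ruled out for the subject.** An earlier value of 400 c/mL or more may already have qualified, and an early-termination value of 400 or more could qualify if it is the last one in a snapshot window. This stands as an exception.
- **The advisory wording at 400 c/mL or more.** Because PDVF testing is stated as an addition to the table's management guidance, a confirmed value at that level is sent whatever the table says. That largely settles the matter; what remains is two instructions for one result.
- **The 400 c/mL level may be deliberate.** Every row that mentions testing starts there, and entry also requires at least 400 c/mL. Stop rules and failure definitions can serve different purposes, and assays may not amplify at 200-399 c/mL. This makes the yield uncertain. It does not explain why a removal for viral load should be absent from the failure tally.

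**Conclusion.** The gap is real and narrow. After Week 48 a confirmed 200-399 c/mL forces discontinuation, meets no PDVF criterion and prompts no resistance test. The PDVF tally and the emergent-resistance tabulation may therefore miss these removals unless discretionary testing is done. Neither the Week 24 primary endpoint nor the Week 96 snapshot endpoints are affected.

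The size of the loss cannot be derived from the protocol. The 2.5% or 5% of an arm rests on an assumed 1 or 2 removals per arm; with none, nothing is lost. It would be tempting to express the loss as a share of all late virologic failures, but that would divide one assumed count by another and should not be quoted. How many of the untested samples would show resistance is also unknown. The change is worth making because it is cheap and because the resistance objective depends directly on the Section 5.4.1 criteria.

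**What to change.** Reconcile Sections 3.5, 5.4.1.1 and 5.4.1.2. No view is taken here on which stopping threshold is right; the changes concern counting and measurement.

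1. State that any subject discontinued under the protocol's own viral-load rule is counted in the virologic-failure tabulation, or is reported on a separate line beside PDVF.
2. State that a resistance sample from such a subject, already stored from the confirmatory or early-termination visit, is sent for testing by rule. Section 8.4.2.2 uses on-treatment isolates, so say which of the two samples is taken first.
3. Report samples that do not amplify as no result, by arm, so that the number tested and the number evaluable are both visible.
4. Align the advisory wording for 400 c/mL or more after Week 48 in Table 5.4.1.1-1 with the statement in Section 5.4.1.2 that PDVF samples will be sent.

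The cost is a few lines of text and a few assays on stored samples, some of which will give no result. The reported late failure count may become slightly less favourable.

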5.5.2 Sparse Pharmacokinetic Assessments

All subjects will provide Sparse PK samples (as part of the regular blood collection) for the assessment of BMS-955176, ATV, RTV and DTG at visit Weeks 4- 24.

Of the five visits (Week 4 - 24), it is requested that the following guidelines are followed:

- At any one visit Week 4 through Week 24, the Sparse PK sample must be collected approximately 24 hours (between 20 and 28 hours) *after* the dose that was taken the morning before and *before* the morning dose is taken on the day of the visit
- At the remaining four visits Week 4 through Week 24, the blood collections may be done without any specific consideration to timing of previous dose administration (taken either the day before the visit or on the day of the visit), though it is critical that the date and time of the most previous dose of study drug is recorded in the eCRF so that the exact interval between dose and blood sampling can be calculated for accurate PK analysis

PK Samples need to be tested on an ongoing basis prior to the Week 24 database lock and analysis.

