Investigational Product(s), Dose and Mode of Administration, Duration of Treatment with Investigational Product(s): Subjects in each arm and per stage will begin QD dosing (in the morning, with a meal) with BMS-955176 in combination with atazanavir (ATV) [with or without ritonavir (RTV)] and dolutegravir (DTG), or tenofovir (TDF) in combination with atazanavir boosted with ritonavir (ATV/r) and DTG, for a duration of 96 weeks.

Stage 1:

- Arm 1: BMS-955176 120 mg QD + ATV/r 300/100 mg QD + DTG 50 mg QD, OR
- Arm 2: TDF 300 mg QD + ATV/r 300/100 mg QD + DTG 50 mg QD

Stage 2:

- Arm 3: BMS-955176 120 mg QD + ATV 400 mg QD + DTG 50 mg QD, OR
- Arm 4: BMS-955176 180 mg QD + ATV 400 mg QD + DTG 50 mg QD, OR
- Arm 5: TDF 300 mg QD + ATV/r 300/100 mg QD + DTG 50 mg QD

Study Phase: 2b

Research Hypothesis: This Phase 2b study will evaluate whether the combination of BMS-955176 with ATV (with or without RTV) and DTG is efficacious, safe, and well-tolerated in HIV-1 infected treatment-experienced adults.

Objectives:

Primary Objective Stage 1

- To assess the antiviral efficacy of BMS-955176 120 mg and a TDF 300 mg-containing arm, each when given in combination with ATV/r 300/100 and DTG 50 mg by determining the proportion of treatment-experienced subjects with plasma HIV-1 RNA < 40 c/mL at Week 24 in Stage 1.

Primary Objective Stage 2

- To assess the antiviral efficacy of two doses (120 and 180 mg) of BMS-955176, each when given in combination with unboosted ATV 400 mg and DTG 50 mg, and to assess the antiviral efficacy of TDF 300 mg when given in combination with and ATV/r 300/100 mg and DTG 50 mg by determining the proportion of treatment-experienced subjects with plasma HIV-1 RNA < 40 c/mL at Week 24 in Stage 2.

Secondary Objectives

- To assess the antiviral efficacy of BMS-955176 Arms, and the TDF-containing Arms (TDF + ATV/r + DTG), by determining the proportion of treatment-experienced subjects with plasma HIV-1 RNA < 40 c/mL at Weeks 48 and 96
- To assess the antiviral efficacy of BMS-955176 Arms, and the TDF-containing Arms, by determining the proportion of treatment-experienced subjects with plasma HIV-1 RNA < 200 c/mL at Weeks 24, 48, 96

- To assess the emergence of HIV drug resistance in samples selected for drug resistance testing (according to criteria outlined in Protocol [Section 5.4.1](#))

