4.5.1.2 Specific Dosing Instructions for Initial Treatment Arm Assignment

In the morning, with a meal, subjects will take the following:

- Arm 1: One pill each from bottles BMS-955176 120 mg, ATV, RTV, and DTG
- Arm 2: One pill each from bottles TDF, ATV, RTV and DTG

- Arm 3: One pill each from bottles BMS-955176 120 mg, DTG, and two pills from bottle ATV (the unboosted dose of ATV is 400 mg, achieved by 200 mg x 2)
- Arm 4: One pill each from bottles BMS-955176 60 mg, BMS-955176 120 mg and DTG, and two pills from bottle ATV (the unboosted dose of ATV is 400 mg, achieved by 200 mg x 2)
- Arm 5: One pill each from bottles TDF, ATV, RTV and DTG

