Procedure	In-clinic Visit Day 1	In-Clinic Visit Optional Week 2 for Intensive PK (Day 12-16)	In-Clinic Visits Weeks 4, 8, 12, 16, 24, 32, 40, 48, 60, 72, 84, 96, and/or Early Termination (ET) (± 5 days)	Phone Visits Weeks 20, 28, 36, 44, 54, 66, 78, 90 (± 5 days)	Notes
Eligibility Assessments					
Inclusion/Exclusion Criteria	X				
Non-Laboratory Safety Assessments					
Full Physical Examination			WK 12, 24, 48, 96/ET		See Section 5.3.1 for requirements
Targeted Physical Examination	X		WK 4, 8, 16, 32, 40, 60, 72, 84		See Section 5.3.1 for requirements
Vital Signs & Physical Measurements	X		X		See Section 5.3.1 for requirements
Adherence Assessments			X	X	Including review of Dosing Diaries
Pre-treatment Events	X				See Table 5.1-1
Adverse Events Assessments	X	X	X		Serious and Non-serious AEs
Concomitant Medications	X	X	X		See Section 5.3.3
ECG	X		WK 4, 12, 24, 48, 96/ET		See Section 5.3.4 for requirements
Pregnancy Test	X	X	X		For females under age 55, an FSH level must be on record to confirm she is not a WOCBP if pregnancy testing is not being performed. If positive urine, request serum hCG quant. on lab requisition.

Table 5.1-2: Short-term Procedural Outline (AI468048)

Procedure	In-clinic Visit Day 1	In-Clinic Visit Optional Week 2 for Intensive PK (Day 12-16)	In-Clinic Visits Weeks 4, 8, 12, 16, 24, 32, 40, 48, 60, 72, 84, 96, and/or Early Termination (ET) (± 5 days)	Phone Visits Weeks 20, 28, 36, 44, 54, 66, 78, 90 (± 5 days)	Notes
Provide WOCBP with Home Pregnancy test kit(s) to be used during the in-clinic visit interval			WK 16, 24, 32, 40, 48, 60, 72, 84		Provide One Kit at Weeks 16 - 40 Provide Two Kits at Weeks 48 - 84 WOCBP subjects perform test Q4 weeks at home and report results to site.
Laboratory Assessments for Safety and Efficacy and Other Endpoints					
Fasting Chemistry	X		X		Fasting overnight
Fasting Lipid Panel	X		WK 4, 12, 24, 48, 96/ET		Fasting overnight
Hematology	X		X		
Urinalysis	X		X		
Fractional Excretion of Phosphorous (FePO4) (Urine creatinine and phosphorus, Serum creatinine and phosphorus)	X		WK 48 and 96/ET		
Plasma HIV-1 RNA	X	X	X		If collecting an HIV-1 RNA at an UNSCHEDULED visit, also collect samples for Resistance and Exploratory Resistance Testing
CD4 and CD8 T-cell counts	X		X		
HBV Surface Antigen			WK 48 and 96/ET		
HCV Serology			WK 48 and 96/ET		Positive HCV Ab will reflex to HCV RNA

Table 5.1-2: Short-term Procedural Outline (AI468048)

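### Section 5.5.2 lets the regular blood draw follow a same-day dose, which is taken with a meal, at visits that require overnight-fasting labs; in a single draw the rules cannot all be kept

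*Protocol*

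**What the plan says.** All references are to Revised Protocol 01 unless stated otherwise.

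- **Section 5.5.2, where the sample sits.** The sparse PK sample is taken "as part of the regular blood collection" from every subject at Weeks 4 to 24. Table 5.1-2 lists these visits as Weeks 4, 8, 12, 16 and 24.
- **Section 5.5.2, the one timed visit.** "At any one visit Week 4 through Week 24, the Sparse PK sample must be collected approximately 24 hours" after the previous morning's dose (20 to 28 hours) and before that day's dose.
- **Section 5.5.2, the other four visits.** "the blood collections may be done without any specific consideration to timing of previous dose administration", and that dose may have been "taken either the day before the visit or on the day of the visit". The date and time of the most recent dose go into the eCRF. Meal status is not mentioned.
- **Section 4.5.1.2, dosing.** "In the morning, with a meal, subjects will take the following"; the instruction covers all five arms.
- **Table 5.1-2, laboratory tests.** Fasting chemistry is marked for every in-clinic visit. The "Fasting Lipid Panel" is due at Weeks 4, 12, 24, 48 and 96. Both rows carry a note asking for an overnight fast.
- **Section 8.4.3, analysis.** Fasting lipids are analysed over time, and the only exclusion named is values after the start of lipid-lowering drugs. Laboratory abnormalities are summarised by toxicity grade.

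**The concern.** Each of the three instructions is workable by itself. The difficulty comes when a site uses the freedom given in section 5.5.2. A subject who has already dosed that morning as instructed has eaten, so the chemistry and lipid samples from that draw are not fasting. A subject who kept the fast and still dosed has taken the drug without food. The protocol does not say which instruction gives way, and it describes no second draw.

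Three uses of the data are exposed:

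- **Lipids.** Section 5.6 names dyslipidemia among the toxicities on which Arms 3 and 4 are set against Arms 1, 2 and 5, and section 1.1.3 expects a better lipid profile without the booster. Fed values mixed into a fasting series blur that comparison.
- **Toxicity grades.** The DAIDS table grades glucose by different limits according to fasting status, and defines the cholesterol, LDL and triglyceride grades for fasting samples.
- **Sparse PK.** These samples feed the population PK and exposure-response models (sections 8.4.4.1 and 8.4.4.2). Section 1.1.2 reports a clear food effect: at 120 mg, AUC was 53% higher with a high-fat meal than fasted. A model that treats every dose as fed would be wrong for some records.

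**Working it through.** No sample-size, power or alpha figure is involved, so the check is a side-by-side reading and a count of visits.

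**Step 1: overlap of the schedules** (Table 5.1-2)

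| Visit | Sparse PK | Fasting chemistry | Fasting lipids |
|---|---|---|---|
| Week 4 | yes | yes | yes |
| Week 8 | yes | yes | no |
| Week 12 | yes | yes | yes |
| Week 16 | yes | yes | no |
| Week 24 | yes | yes | yes |

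**Step 2: visits open to a same-day dose.** Five visits less the one timed visit: 5 - 1 = 4. All four carry fasting chemistry.

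**Step 3: lipid panels among the open visits.** It depends on where the timed sample falls.
- Timed sample at Week 8 or 16: all 3 lipid visits are open.
- Timed sample at Week 4, 12 or 24: 3 - 1 = 2 lipid visits are open.

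**Step 4: what each sequence does to the rules**

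| Sequence on the visit day | Overnight fast kept? | Dose with a meal? | Allowed by 5.5.2? |
|---|---|---|---|
| Single draw, then dose with a meal | yes | yes | yes |
| Dose with a meal, then single draw | no | yes | yes, at four visits |
| Dose without food, then single draw | yes | no | yes, at four visits |
| Fasting draw, dose with a meal, second draw for PK | yes | yes | not described, not excluded |

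Section 5.5.2 accepts the second and third rows on PK timing, and each breaks a rule stated elsewhere.

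**Step 5: does fasting status change a grade?** The laboratory limits are readable in Appendix 3 of the original protocol, and the revised protocol cites the same version of the DAIDS table. A glucose of 140 mg/dL is Grade 1 if nonfasting (116 to 160) and Grade 2 if fasting (126 to 250). The protocol does not list the components of the chemistry panel, so this example assumes that glucose is one of them.

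**Step 6: where the conflict comes from.** The original section 5.5.2 put every sparse sample before the morning dose, which fits a fasting draw followed by a dose with food. Amendment 04 relaxed this to one visit, and section 3.1.4 was changed to match. The fasting notes and the meal instruction stayed. The conflict therefore lies among passages that are all in force.

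**The case against.** The strongest reply is that section 5.5.2 grants a freedom and imposes nothing. It is worded as a request to follow guidelines, relaxes PK timing only, and does not waive the overnight fast. A site that draws before the day's dose satisfies every instruction. This stands, and it makes the count in the working a ceiling.

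A second reply is that belonging to the regular collection need not mean one venipuncture; a fasting draw followed by a later PK draw would fit the text. That also stands, although no such sequence is set out.

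A third is that the data may already reveal the problem. Dose time is recorded and section 5.5 asks for the exact sample time, so a same-day dose before the draw marks a probably fed sample. The eCRF, laboratory manual and SAP are not available here and may hold explicit fields or rules. This stands in part: dose time does not say whether the subject ate.

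Two stronger readings are tempting and should be resisted.

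- A reader might invert the food-effect ratios and take the result as the exposure lost in the affected PK samples. Those ratios compare fed with fasted dosing. Here only the visit-day dose would be fasted, at steady state, with a half-life of about 35 hours (section 1.4.1.3). In a simple linear one-compartment model with rapid absorption, carry-over across 24 hours is 2^(-24/35) = 0.62. The visit-day dose then supplies only about 1 - 0.62 = 38% of that interval's AUC, so the shift is much smaller than the raw ratios suggest.
- A reader might infer bias between arms because the trial is open-label. Nothing in the protocol suggests that sites would time draws differently by arm.

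**Conclusion.** The point holds as a minor inconsistency in the current protocol. The freedom in section 5.5.2 cannot be used in a single draw without breaking either the fasting note in Table 5.1-2 or the meal instruction in section 4.5.1.2. At most four of the five visits from Week 4 to Week 24 are affected, with two or three of the three early lipid panels. The actual number depends on how often subjects dose before the draw, which the protocol does not let one estimate; it could be zero.

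The consequence is limited to two things: non-fasting values entering fasting-lipid summaries and fasting-based grades without a mark, or a sparse PK sample that reflects a dose taken without food. The primary endpoint, HIV-1 RNA below 40 c/mL at Week 24, is not affected. The Week 48 and Week 96 lipid panels lie outside the sparse PK period. It would be too strong to say that the fasting labs or the dosing condition are broken as a matter of course, since a pre-dose draw or a split draw keeps every rule. The conclusion assumes one draw per visit and no overriding instruction in documents that are not shown.

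**What to change.** 1. Reconcile section 5.5.2, Table 5.1-2 and section 4.5.1.2. The sponsor decides which instruction governs on visit days from Week 4 to Week 24, or whether the fasting and PK draws are separated, and states it in one place.
2. If not already captured, record fasting status with each chemistry and lipid sample, and the meal status of the last dose with each sparse PK sample.
3. In section 8.4.3 or the SAP, restrict analyses labelled as fasting to samples confirmed as fasting, and apply fasting-based grades on the same basis.

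The cost is a short wording change and at most two eCRF fields. The downside is that some lipid values will drop out of the fasting analysis.
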